11.	Risks to Subjects/NSR Determination	12
12.	Potential Benefits to Subjects	13
13.	Alternatives to Participation	13
14.	Confidentiality	
15.	Adverse Event Reporting	
16.	Statistical Considerations	
17.	Data Management	15
18.	Study Monitoring.	
19.	Regulatory Requirements	15
20.	Personnel Responsibilities	
20.1	*	
20.2	1 0 1	
Refere	nces	

VERSION DATE: 9/8/21

1. Introduction, Background and Rationale

Newborn metabolic acidosis is a condition that can result in debilitating sequelaesuch as brain injury, renal insufficiency, pulmonary hypertension, necrotizing enterocolitis, hypoxic-ischemic encephalopathy, and cerebral palsy, ². During gestation, labor and delivery, fetal oxygenation is dependent on placental oxygen transfer to the fetus. The rate and effectiveness of this oxygen delivery process is affected by numerous factors, including maternal partial pressure of oxygen, maternal blood oxygen content, blood flow in the uterine circulation, fetal blood oxygen content and umbilical blood flow, the relative affinities of fetal and maternal hemoglobin for oxygen, permeability and surface area of the placental barrier, and placental oxygen consumption.³ Initially, compromised oxygen delivery to the fetus can be tolerated and compensated for by increased oxygen extraction and reduction of blood flow to non-essential organs. However, the fetus has limited ability to increase placental blood flow³. When the fetal oxygen saturation falls below 30% for 10 minutes, the fetus begins suffering hypoxia-ischemia and anaerobic metabolism results in the formation of lactic acid, decreasing blood pH. Newborn metabolic acidosis is the clinical presentation of prolonged fetal hypoxia-ischemia (i.e., insufficient oxygenation of the fetus).⁴ This decrease in blood pH due to oxygen deprivation has been described as fetal blood oxygen saturation percentage of <30%⁵ (hemoglobin that is bound to oxygen divided by total hemoglobin). Prolonged oxygen deprivation then results in the development of a metabolic (lactic) acidosis. When insufficient oxygenation is prolonged and further acid is formed, the fetus is at increased risk of morbidity.⁶

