The device shipments/delivery and request for return will be the responsibility of the Sponsor. The device is not delivered to the site until IRB approval has been obtained. The Investigational device is precommercialization and will not be available to study subjects after participation in the study. Study subjects will not be restricted from use of any medication or other substance while participating in the study. In addition to the PI and co-investigators, members of the Raydiant Oximetry team may transport and be accountable for the investigational device.

10. Data Collection

In addition to specific LUMERAH device and cardiotocography data, the following data is the minimum subject data set to be collected during this study:

- Maternal demographics such as race, ethnicity, age, parity, prior perinatal outcomes, height, weight (to calculate BMI), number and date of prior cesarean deliveries, Maternal Vital Signs such as the maternal heart rate and maternal oxygen saturation.
- CTG Tracings to be downloaded from the EMR
- Location on maternal abdomen for best signal quality
- Safety data (see "Adverse Event Reporting" below)

In addition, the internal sensor data will be analyzed and compared to the LUMERAH device data. We will report the mean error, standard deviation of difference and root-mean square error from the study results. In addition, we will present a scatter plot (with the identity line and Deming regression line), a Bland-Altman plot [with the 95% limits of agreement (LoA)] and report the repeatability and reproducibility by providing a population mean bias (μ 0), between-subject variance (σ 2) with our final statistical analyses.

Neonatal outcomes will not be collected during this study.

11. Risks to Subjects/NSR Determination

A significant-risk (SR) device study is defined by the United States Food and Drug Administration (https://www.fda.gov/media/75459/download) as one that:

- Is intended as an implant and presents a potential for serious risk to the health, safety, or welfare of a subject;
- Is purported or represented to be for use supporting or sustaining human life and presents a potential for serious risk to the health, safety, or welfare of a subject;
- Is for a use of substantial importance in diagnosing, curing, mitigating, or treating disease, or otherwise preventing impairment of human health and presents a potential for serious risk to the health, safety, or welfare of a subject;

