This is an observational, noninvasive study with primary endpoints related to the LUMERAH device correlation with the Nellcor device and internal sensor (manufactured by Axcesor). Raydiant Oximetry met with the FDA on Feb 11, 2020 and suggested that we power our pilot and pivotal studies for specificity, and not sensitivity, because poor specificity of CTG technology is the unmet clinical need in obstetrics. CTG technology has a 29% specificity and the FDA agreed with this approach. Seelbach-Gobel²³ demonstrated that the Nellcor fetal pulse oximetry device had a specificity of 65% for the detection of newborn metabolic acidosis. The incidence of newborn metabolic acidosis has been reported to be 2-4% and the incidence of hypoxic fetuses is 3-4%. Our sample size calculations are based on a significance level of 0.05 (i.e. type 1 error=0.05) with the goal to achieve power of 0.8 and a lower confidence level of 80% to establish a clinical proof of concept. The sample size calculation, under these assumptions, is 48 subjects for this pilot study.

VERSION DATE: 9/8/21

To compare the Nellcor N-400 device output to the LUMERAH output, we are following the FDA guidance document (dated March 4, 2013) for pulse oximeters, where the in-vivo validation set should include at least 200 data points from 10 or more human subjects. Per the FDA recommendation, we will report the root mean square (RMS) error and produce a scatter plot with the identity line and a Deming regression line. In addition, we will report a Bland-Altman plot with the 95% limits of agreement as well as the 95% confidence intervals for the limits of agreement.

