Our preclinical data set for algorithm training required approximatively 300 data points from 20 sheep. We expect that a similar amount of human data sets will be required for algorithm training and then another 10 human subjects will be enrolled for prospective algorithm validation of the LUMERAH device. Therefore, the absolute *minimum* required sample size to compare Nellcor N-400 device output to the LUMERAH output is 30 subjects. However, we will calibrate and validate on up to 60 patients to ensure that we can identify hypoxic fetuses. East et al²⁴ reported that 3.9% of observations with the Nellcor N-400 technology displayed fetal oxygen saturations below 30%. Therefore, enrolling and following 60 subjects allows the opportunity to monitor and study approximately two hypoxic fetuses. We intend to collect up to 60 of these "ground truth" cases with varied oxygenation levels before proceeding to PILOT 2. With the expectation that we will have to consent an additional 50% who may not meet the inclusion/exclusion criteria, the total number consented will be a maximum of 90 subjects.

17. Data Management

Only individuals approved by the Sponsor and who have adequate training in the use of the Investigational device are given authorization of access to perform the measurement and record the data. The data collected will be marked with a study ID number to protect confidentiality of each subject.

Only the research staff will have access to the link between the study ID and the patient's identifying information. The key will be stored in a password-protected document on a restricted access folder on the hospital network. Only the PI/Co-I and research team will have access to this document.

A separate document listing only study ID numbers will be stored on a password-protected document on a restricted access folder on the hospital network. This will contain the subjects' de-identified obstetric and medical history as relevant for the project. Data will be submitted to the sponsor through an electronic, secure database.

18. Study Monitoring

This study will be monitored for data accuracy and adherence to the protocol by the Sponsor's representative and/or a 3rd party qualified monitor. It is expected that there will be frequent attendance of the Sponsor's representative at the study site. Major protocol deviations will be reported to the Sponsor immediately and the IRB at the required reporting intervals.

19. Regulatory Requirements

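### Agreement is summarised by one pooled bias and one set of limits of agreement, with no check that either holds near the 30% saturation the protocol treats as hypoxia

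*Combined protocol and SAP*

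**What the plan says.** Concurrence with the N-400 is the primary efficacy endpoint (Synopsis). Section 16 states that "we will report a Bland-Altman plot with the 95% limits of agreement as well as the 95% confidence intervals for the limits of agreement". It also asks for an RMS error and says the sponsor will "produce a scatter plot with the identity line and a Deming regression line". Section 10 lists the same plots together with the average error and the SD of the differences, and says the study will "report the repeatability and reproducibility by providing a population mean bias" and a between-subject variance. Each numerical summary of agreement is pooled over all saturations. The text does not specify the form of the limits, but one set with confidence intervals most naturally means a constant band.

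Neither section prespecifies a check that bias or spread is constant, limits that vary with level, or results for low readings. Yet Section 1 attaches special meaning to one level: "When the fetal oxygen saturation falls below 30% for 10 minutes", the fetus is said to begin suffering hypoxia-ischemia. Section 16 extends enrolment to 60 so that hypoxic fetuses can be identified, citing an earlier study in which "3.9% of observations with the Nellcor N-400 technology displayed fetal oxygen saturations below 30" per cent.

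**The concern.** Standard limits, mean difference ± 1.96 SD, cover 95% of differences overall. They cover 95% at each saturation only if the mean and spread of the differences are the same throughout the range.

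There is a plausible reason why they may not be. Section 16 expects that "a similar amount of human data sets will be required for algorithm training", the preclinical set being about 300 points. At the cited rate, few of those would be below 30%. A fit that minimises squared error on such data pulls predictions toward the centre, so low values read high and high values read low, while the overall mean bias stays near zero. A pooled bias near zero with a pooled band would then be read as the error at 30%. The actual error there would be shifted upward, which could make a poorly oxygenated fetus look better oxygenated than it is. A confidence interval around the pooled band does not address this.

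**Working it through.** **The plan's own figure.** 60 × 0.039 = 2.34, which reproduces Section 16's statement that "enrolling and following 60 subjects allows the opportunity to monitor and study approximately two hypoxic fetuses". The complement is 1 − 0.039 = 96.1% at or above 30%. At the same rate:

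- Training set of about 300 points: 300 × 0.039 = 11.7 readings below 30%.
- Validation set of 200 points (Section 16's minimum, from 10 or more subjects): 200 × 0.039 = 7.8 readings.
- If 3.9% is applied per fetus, as Section 16 does, the chance of no hypoxic fetus among 10 validation subjects is 0.961^10 = 0.67.

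**Illustrative model.** These inputs are assumptions, because the documents give no SDs, training method or R-squared. The N-400 value X is normal with mean m = 45 and is error-free. With 3.9% below 30 (normal quantile 1.762), the SD is s = (45 − 30)/1.762 = 8.51. LUMERAH is a least-squares prediction, Y = m + R²(X − m) + e, with SD(e) = s√[R²(1 − R²)].

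- Pooled limits: ± 1.96 · s√(1 − R²). With R² = 0.5, ± 1.96 × 6.02 = ± 11.8.
- Bias at X: (1 − R²)(m − X). At X = 30, 0.5 × 15 = +7.5.
- Spread at fixed X: 8.51 × 0.5 = 4.26.
- Share outside the pooled limits at X = 30: P[Z > (11.8 − 7.5)/4.26 = 1.01] = 15.6%. The lower tail is negligible.

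| R² | Pooled limits | Bias at 30% | SD at fixed X | Outside limits at 30% |
|---|---|---|---|---|
| 0.3 | ± 14.0 | +10.5 | 3.90 | 18.8% |
| 0.5 | ± 11.8 | +7.5 | 4.26 | 15.6% |
| 0.7 | ± 9.1 | +4.5 | 3.90 | 11.7% |

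The last column does not depend on the assumed mean. Once 3.9% is fixed, bias, spread and limits all scale with s, and the cut-off is (1.96 − 1.762√(1 − R²))/√R². The bias in points does depend on it: with R² = 0.5, it is 0.5 × (40 − 30) = +5.0 for a mean of 40 and 0.5 × (50 − 30) = +10.0 for a mean of 50.

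**On the Bland-Altman axis.** With R² = 0.5, the slope of the difference on the two-device mean is [(0.5 − 1)/2] ÷ [(1 + 0.5 + 2 × 0.5)/4] = −0.25/0.625 = −0.40. At a two-device mean of 30, bias is −0.40 × (30 − 45) = +6.0. The residual SD is 8.51 × √(0.5 − 0.25²/0.625) = 5.38, giving limits of −4.6 to +16.6. The share outside ± 11.8 is about 14%.

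**Second model, by simulation.** True saturation was given an SD of 8 to 12 with 3.9% below 30, sensor noise an SD of 4 to 10 points, and the algorithm was the least-squares prediction. The pooled limits covered 95% overall. Where the reference was below 30%, mean over-reading was +2.6 to +10.8 points and coverage 66% to 91%, with nearly all misses above the upper limit. In the central case (SDs of 10 and 6), limits were ± 10.1, bias +5.7, coverage 83% and Deming slope 0.84.

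**Null case.** If the difference is unrelated to true saturation and has constant spread, the pooled limits cover 95% at every level.

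**The case against.** The mechanism is conditional. The documents state no training method, weighting or saturation sampling. The 3.9% comes from a cited earlier study, not this trial's training set. The algorithm was first derived in sheep whose oxygenation was manipulated (Sections 1 and 9), and Section 16 seeks cases at varied oxygenation levels. All of this stands, and it limits what can be claimed.

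A reader might infer that LUMERAH will over-read low values and that the planned limits are therefore wrong there. The documents do not support that: the null case above is compatible with everything they say. A reader might also take a figure further down the range. At an N-400 value of 25%, the same model with R-squared of 0.5 puts 34% outside the limits. But the protocol's level is 30%, where the figure is 16%, and under this model only about 0.9% of readings lie below 25%.

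The planned scatter plot, Deming line and Bland-Altman plot can reveal a trend with level. They do not change the reported limits, and no interval for the slope or consequence of a trend is stated.

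Regressing the difference on the two-device mean has its own weakness. Unequal device variances alone produce a slope, even when LUMERAH is unbiased at every true level. Regressing on the N-400 value has the opposite weakness, because error in the N-400 creates a slope. Neither regression should therefore replace the planned limits on a significance test.

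Finally, this is a pilot whose readings guide no care, and low readings will be few. That bears on precision, not on whether the check should be specified.

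**Conclusion.** The plan omits a check that matters for its primary efficacy endpoint, and the pooled limits may understate over-reading near 30%. The omission is in the text; its consequence is conditional. Under shrinkage toward the mean, with the assumptions stated, bias at an N-400 value of 30% is about +7.5 points and about 16% of readings fall outside nominal 95% limits (12% to 19% for R-squared of 0.7 to 0.3). If error is unrelated to saturation, nothing is lost. More enrolment would narrow the interval around a pooled band without making it specific to a level. The addition is worth making, and it does not invalidate the planned analysis.

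**What to change.** Keep the planned limits. Add to Section 16, without a significance gate:

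- A mixed model of the difference (LUMERAH minus N-400) on saturation level, with a random intercept per woman and a model for how spread changes with level.
- The slope with its 95% CI.
- Bias and 95% limits of agreement, each with CIs, at stated saturations such as 30, 40, 50 and 60%.
- The mean of the two devices as the main axis, with the N-400 value as a sensitivity analysis, since each axis can create a slope by itself.

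Align Section 10 with this wording. No new subjects, visits or measurements are needed. The cost is a little more analysis, and wide, possibly less favourable limits at low saturation, where about 8 of 200 validation readings are expected at the cited rate. Estimates at 30% will lean on the fitted line from higher values, and the report should say so.

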VERSION DATE: 9/8/21

STUDY TITLE:

Trans-abdominal fetal pulse oximetry: PILOT 1

STUDY SPONSOR:

Raydiant Oximetry, Inc. [name]

Version No.	Version Date	Modifications
V1	3/15/21	N/A- Original Release
V2	4/9/21	Added exclusion criteria to correspond
		with Nellcor IFU
V3	6/7/21	Clarification of inclusion induction/active
		labor enrollment, timing& removal device,
		Amazon card replaced with UTMB
		Clincard, defined health provider
		(physician, midwife, nurse practitioner,
		nurse)
V4	7/14/21	Additional clarifications added in the
		Background, Procedures, and Risks
		Sections.
		Added that internal sensor previously
		manufactured by Nellcor, is now
		manufactured by Axcesor. Clarification on
		enrollment and sensor comparison
		statistics.
V5	9/8/21	Remove reference to sterile sleeve, replace
		words to indicate internal sensor is
		sterilized.

VERSION DATE: 9/8/21

Study Synopsis

Title: Trans-abdominal fetal pulse oximetry; PILOT 1

Study Design: Prospective, observational, investigator-blinded study.

Study Device: The Raydiant Oximetry Sensing System (LUMERAH)

Objectives: 1) Assess safety and performance of the LUMERAH device as an adjunct to cardiotocography; 2) Assess human factors, device usability factors, and signal capture; and 3) Compare device output to "ground truth" technology (Nellcor N-400 with internal sensors manufactured by Axcesor).

Safety Endpoints

Rate of device-related adverse events such as erythema or rash on the maternal abdomen at the location of the sensor. Note: In this study, use of the device provides additional clinical information, but clinical judgement is based on standard fetal monitoring, including cardiotocography, and investigators are blinded to oximetry readings. The maternal skin at the sensor site will be examined intra and postpartum.

Effectiveness Endpoints

Primary efficacy endpoint is concurrence of oximetry readings compared to those of the Nellcor N400 System ("ground truth").

Study Populations:

Up to 60 pregnant women. who are/have:

- 1) Willing and capable to provide informed consent
- 2) Age \geq 18 years
- 3) BMI < 50 (with no more than 4 cm between maternal skin and fetal skin)
- 4) Gestational age > 36 weeks
- 5) Singleton pregnancy
- 6) Vertex presentation
- 7) Active labor
- 8) Category I or Category II tracings
- 9) Ruptured amniotic sac with cervical dilation of ≥ 2 cm and a station of -2 or lower

Exclusion Criteria

- 1) Age < 18 years

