- 2) BMI > 50 third trimester
- 3) Gestational age < 36 weeks
- 4) Multiple gestation
- 5) Nonvertex fetal presentation
- 6) Suspected vasa previa
- 7) Latent labor
- 8) Category III CTG tracing (i.e., need for immediate delivery)
- 9) Fetal anomalies and/or chromosomal disorders
- 10) Chorioamnionitis
- 11) Placenta Previa

VERSION DATE: 9/8/21

12) History of HIV, Genital Herpes, or other infection precluding internal monitoring

13) Unable to provide informed consent (e.g., cognitively impaired)

Description of Device and Study Intervention Including Non-Significant Risk Determination:

The Raydiant Oximetry Sensing System (LUMERAH) is a non-invasive fetal pulse oximeter that measures fetal arterial oxygen saturation using safe, non-invasive, transabdominal near-infrared spectroscopy. The LUMERAH device is intended as an adjunct to cardiotocography by detecting decreases in fetal oxygenation. In this study, women in labor will be simultaneously monitored with proven (previously FDA-approved) technology as a "ground truth". These women will be simultaneously monitored with the LUMERAH device and the Nellcor N-400 device. Obstetric healthcare providers are blinded to oximetry data presented by both devices; therefore, clinical decisions regarding interventions are made based on the standard factors, including cardiotocography. The primary efficacy analysis will be performed retrospectively by comparing data of fetal oxygenation displayed and recorded by both devices. It is the opinion of the Sponsor that this device and study design, including the placement of the sterile internal sensor after membrane rupture, pose no significant risk to the mother or fetus. Further, to mitigate any chance of dystocia, the internal sensor will be placed for 6 hours or less. There is no change to standard of care procedures for fetal heart rate monitoring. The fetal heart rate that will be monitored with the Investigational device will be used for research purposes only. Results of either the LUMERAH sensor or the internal sensor will not be used to guide or alter patient management.

Table of Contents

1.	Introduction, Background and Rationale	5
2.	Objectives	
3.	Study Design, Recruitment Methods, Investigator/Team Training and Timeline	7
4.	Enrollment Criteria:	8
5.	Withdrawal of Subjects	9
7.	Duration of Subject Participation	9
8.	Payment to Subjects/Cost of Participation	10
9.	Study Procedures/Device Use	
10.	Data Collection	

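### Section 16 plans training and then validation, but gives no split or algorithm lock for up to 60 subjects and does not confine the agreement figures to subjects outside training

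*Combined protocol and SAP*

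**What the plan says.** The Synopsis (Effectiveness Endpoints) makes agreement with the N-400 the main outcome: "Primary efficacy endpoint is concurrence of oximetry readings compared to those of the Nellcor N400 System". Its device description adds: "The primary efficacy analysis will be performed retrospectively by comparing data of fetal oxygenation displayed and recorded by both devices".

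Section 16 cites a guidance minimum under which "the in-vivo validation set should include at least 200 data points from 10 or more human subjects". It then lists RMS error, a Deming regression line and Bland-Altman limits with confidence intervals. Next it explains the numbers. About 300 points from 20 sheep were needed for preclinical training, a similar amount of human data is expected, and "then another 10 human subjects will be enrolled for prospective algorithm validation of the LUMERAH device". From this it concludes that the minimum "required sample size to compare Nellcor N-400 device output to the LUMERAH output is 30 subjects". The following sentence is "However, we will calibrate and validate on up to 60 patients to ensure that we can identify hypoxic fetuses".

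Section 10 says of the same comparison: "We will report the mean error, standard deviation of difference and root-mean square error from the study results". Section 9 uses the internal sensor in every subject and plans about 40 data sets per subject. It describes the algorithm under test as derived from work in pregnant sheep. Sections 1 and 16 have the algorithm trained on the human data of this study.

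**The concern.** The N-400 reading is both the target for training and the reference for judging the device. Error measured in subjects whose reference values helped to fit the algorithm is usually smaller than error in new subjects. The plan recognises this by setting 10 later subjects aside. That separation is explicit only at the 30-subject minimum. At any larger number the text does not say who is training, who is validation, when the algorithm stops changing, or which group supplies the reported figures.

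At stake is how the primary endpoint is read. Section 16 has PILOT 2 following this study, and Section 12 says the results may refine later studies and device development. An RMS error that mixes fitted and unfitted subjects, or several algorithm versions, is a poor basis for that planning.

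**Working it through.** **1. The plan's own figure.** Section 16's minimum of 30 reproduces as 20 (a human training set matched to 20 sheep) + 10 (validation) = 30. The 20 is inferred from 30 - 10; the plan does not state it for humans.

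**2. Does any sentence restrict the analysis set?**
- Synopsis, endpoint and primary analysis: no subset named.
- Section 10: error figures come from the study results, with no subset named.
- Section 16, guidance paragraph: refers to a validation set just before listing the statistics, but does not say they are computed in that set alone.
- Section 16, sample-size paragraph: training and validation subjects together are the number needed for the comparison. For up to 60 there is one pool and two purposes.
- No section mentions a locked version, a rule assigning subjects, or what follows if the algorithm is retuned.

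**3. Training share if the groups were pooled.** Share = training subjects / N.

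| N | Training / validation | Training share |
|---|---|---|
| 30 | 20 / 10 | 20/30 = 67% |
| 60 | 20 / 40 | 20/60 = 33% |
| 60 | 50 / 10 | 50/60 = 83% |

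If the similar amount of data means about 300 data sets, then at 40 per subject training needs 300/40 = 7.5, about 8 subjects. The share at 60 could then be as low as 8/60 = 13%.

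These are shares of subjects, not effects on RMS error. RMS error weights data points, and Section 9 allows anything from a few data sets to about 40 per subject.

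**4. What pooling would do, under assumptions.** With equal points per subject and training share w, pooled RMSE = sqrt(w × RMSE_train² + (1 - w) × RMSE_val²). Suppose re-processed training subjects have an RMSE of 0.9, 0.8 or 0.7 of the validation value (assumed; not in the documents). Pooled RMSE relative to the validation value is then:
- 20/40 split: 0.97, 0.94 or 0.91
- 50/10 split: 0.92, 0.84 or 0.76

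The form and complexity of the algorithm are not given, so this range is illustrative.

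**5. Which output is compared?** The Synopsis speaks of data displayed and recorded. A value displayed during labour cannot have been fitted to that same subject's N-400 readings. If early subjects contribute live output from the sheep-derived algorithm, pooling mixes versions, and RMS error could be too high or too low.

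**6. Is a validation-only analysis feasible?** 10 × 40 = 400 data sets against 200 points. An average of 200/10 = 20 per subject is enough. This assumes that one data set counts as one data point, which the documents do not define.

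**7. Hypoxic fetuses in a validation set.** With Section 16's per-fetus incidence of 3-4%, the chance of none among n subjects is 0.96^n to 0.97^n:
- n = 10: 66-74%
- n = 20: 44-54%
- n = 40: 20-30%

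Section 16's 3.9% is a share of observations, so it is not used here as a rate per subject.

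**The case against.** The best defence is that a hold-out is already there in substance. The statistics in Section 16 follow directly on a sentence about the validation set, so the natural reading is that they belong to it. Enrolling 10 more subjects after training, for prospective validation, implies different people and an algorithm that exists before they arrive. Counting 20 + 10 as the number needed to carry out the comparison need not mean that both groups enter the statistics.

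Much of this stands. A reader might infer that the sponsor plans to test the device on its own training data. The documents do not say so; pooling is left open, not planned. A reader might also infer that RMS error will certainly be too low. That needs two conditions, pooling and re-processing of training subjects' signals with the human-trained algorithm, and the text establishes neither.

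The defence does not supply a split above 30 subjects, a lock, or a sentence overriding Section 10's broader wording. Blinding does not help, because it covers investigators and obstetric providers, not algorithm developers. Sponsor staff may be present at data capture (Section 14), data go to the sponsor (Section 17), and the sponsor is responsible for review and analysis (Section 20.2).

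**Conclusion.** The point holds as a gap in the specification of the primary agreement analysis that should be closed. Applied as written, the Synopsis and Section 10 admit training subjects to the primary figures, and the hold-out is defined only at 30 subjects.

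Optimistic bias is conditional on both pooling and re-processing. If live output is pooled instead, the figures mix versions and the direction is not known. The size cannot be derived from the documents. The 67% and 33-83% shares rest on the inferred 20-subject training set and fall if about 8 subjects are enough.

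It would go too far to say that a pass/fail decision or patient care is compromised. No acceptance limit is stated, and readings are not used in management. The effect is on interpretation and on planning of later work.

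**What to change.** In Section 16, and by cross-reference in the Synopsis and Section 10:

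- State that the primary mean bias, RMS error and limits of agreement use only data that are out-of-sample at subject level. This means validation subjects, at least 10 with at least 200 data points.
- Pre-specify how subjects are assigned to training or validation for any total up to 60.
- Lock a named algorithm version before the developers use validation subjects' N-400 values.
- Report training-set figures separately, labelled in-sample. Subject-level cross-validation over all subjects may be added as a secondary analysis.
- Say which version is evaluated, and whether the output is live or re-processed. Reconcile Section 9 (sheep-derived) with Sections 1 and 16 (trained on human data).

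No extra subjects are needed within the cap of 60. The costs are fewer points in the headline estimate, a possibly less favourable RMS error, and a real data-access control at the sponsor, since wording alone will not keep reference values from the developers. A small validation set may also contain no hypoxic fetus (66-74% chance with 10 subjects). A larger one lowers that chance but leaves fewer subjects for training, so the sponsor should choose the ratio in advance with both in view.
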